37. Phone follow-up if permission granted by participants. Submit later.						X
38. Modified Scale for Suicidal Ideation (MSSI) – to be used as needed e.g., for triage evaluation acute suicide risks in addition to the C-SSRS	X	X	X	X	X	X
39. UCSD Brief Assessment of Capacity to Consent (UBACC)	X					X
40. Anxiety Timeline	X			X	X	X
41. Peterson Puberty Scale.PPS-Male	X			X	X	X
42a. Self-Compassion Scale (SCS) 42b. the Self Compassionate Reactions Inventory.	X			X	X	X
43. Adolescent Life Experience Survey	X			X	X	X
44. Hopelessness Scale for Children (HSC)	X	X	X	X	X	X
45a. Dimensional Anhedonia Rating Scale (DARS) 45b. Temporal Experiences of Pleasure Scale (TEPS) 45c. Positive and Negative Affect Schedule (PANAS)	X		X	X	X	X
46. Brown_Stanley Safety Plan Template	X			X	X	X
47. Suicidal Circumstances Schedule	X			X	X	X
48. Suicide Attempters Risk	X			X	X	X
49. Suicide Attempters Intent	X			X	X	X
50. Phone suitability screen script						
51. Rosenberg's Self-Esteem Scale (RSES)	X			X	X	
52. Dissociation Experience Scale (DES-2)	X	X	X	X	X	
53. Dissociation Tension Scale (DSS)	X	X	x	X	X	
54. Borderline personality questionnaire (BPQ)	X			X	X	
55. Revised Conflict Tactics Scale (CTS2)	X					
56. California Psychotherapy Alliance Scales (CALPAS)	X					
57. Working Alliance Inventory (WAI)	X					
58. Working Alliance Inventory – Short Revised (WAI-SR)	X					
59. Experiences in Close Relationships-Revised (ECR-R)	X			X	X	
60. Structured Clinical Interview for DSM-5 Personality Disorder (SCID-5-PD)	X			X	X	X

61. Structured Clinical Interview for DSM-5 Clinician Version (SCID-5-CV)	X			X	X	X
62. Minnesota Multiphasic Personality Inventory-Adolescent (MMPI-A- RF)	X			X	X	X

Study Duration: Approximately 5 - 18 months.

5.2 The duration anticipated to enroll all study participants: 5 -10 years.

5.3 The duration to complete all study procedures, long-term follow-up, data analysis: 14 - 20 years.

5.4 Use of radiation: No use of radiation.

5.5 Use of Center for Magnetic Resonance Research: Yes.

6. Data and Specimen Banking: N/A.

6.1 Not applicable.

7. Sharing of Results with Participants

7.1 Results will not be shared with participants unless guardians/parents/caregivers specifically request them in writing (via email to the PI). If so, a summary of key questionnaires, (i.e., one paragraph) will be emailed to the caregiver from [contact]. No unscored or "raw" protocols will be shared to preserve test integrity and to avoid confusing patients or

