(7) We will utilize social media accounts (such as: **Facebook**, **Twitter**, **Instagram**, **Tick-Tock**, **independent website**, etc.) to create an informative space about research opportunities and information about the study. These platforms will also be used to disseminate interim findings and progress with participants. Digital media accounts for the “Health and Emotions in Participants Trajectories (**HEAT**) Lab” will be used for this study. A coordinating website “**HEAT Lab**” or **TBT** study standing for (**Teen Brain Training**) will describe participation information, including inclusion and exclusion criteria and amount of time to complete study (Note: This may be the department webpage instead of an independent website). The website and media pages will provide study team contact information and IRB approval number. Potential participants will be advised to contact the research team directly via phone, text, or email for additional information about this study. The lab will include the following disclosure: *“Disclaimer: The information on this site is not intended or implied to be a substitute for professional medical advice, diagnosis, or treatment. All content, including text, graphics, images, and information, contained on or available through this website, is for general information purposes only. Please contact your physician to form a plan that addresses you or your child’s specific needs”* wherever space is allotted.

Note: If at the time of this protocol submission we do not have an independent website, we will submit the link to the site in a future modification. **The independent web site will not go live until we have official IRB approval.**

(7) We will use advertisements on digital media platforms to reach our research population via demographic and key words. An interested individual's click will bring them to a link (e.g., a landing page, study website, psychiatry website, and digital media page) which describes the study and has a link to a REDCap survey. The REDCap survey asks for contact information, birth date of the potential participant, and if they have met the criteria to participate in the study. Qualified potential participants will be then contacted and screened for eligibility for the study.

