suicide ideation on psychometrically valid instruments (SIQ, C-SSRS); (b) random assignment, in the R33 phase, to active NF or to a Unrelated area NF condition; (c) use of HCP Lifespan imaging parameters on a Siemens 3.0 Tesla Prisma scanner, currently the best platform for high-resolution brain imaging; and (d) making all data and analytic algorithms available on a yearly basis for ready access by the wider scientific community using the GitHub platform. Full access to all data is the best means of assuring rigor and reproducibility; (e) although MDD and PTSD disorders afflict females more frequently than males, we intend to enroll both genders to explore the effect of biological variables on responses to NF training.

19. Health Information and Privacy Compliance

19.1 Select which of the following is applicable to your research:

My research does not require access to individual health information and therefore assert HIPAA does not apply.
 I am requesting that all research participants sign an approved HIPAA Disclosure Authorization to participate in the research (either the standalone form or the combined consent and HIPAA Authorization).

This will include HIV/AIDS, genetic testing, mental health diagnosis/treatment records, drug & alcohol abuse or sickle cell anemia status of the offspring/participants participating in research because these conditions/statuses can affect brain function and intellectual achievement in IQ tests, and we need to control for them.

I am requesting the IRB to approve a Waiver or an alteration of research participant authorization to participate in the research.

Appropriate Use for Research:

An external IRB (e.g., Advarra) is reviewing and we are requesting use of the authorization language embedded in the template consent form in lieu of the U of M stand-alone HIPAA Authorization. Note: External IRB must be serving as the privacy board for this option.

19.2 **Identify the source of Private Health Information you will be using for your research (Check all that apply)**

I will use the Informatics Consulting Services (ICS) available through CTSI (also referred to as the University's Information Exchange (IE) or data shelter) to pull records for me

I will collect information directly from research participants.

I will use University services to access and retrieve records from the Bone Marrow Transplant (BMPT) database, also known as the HSCT (Hematopoietic Stem Cell Transplant) database.

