Data Sharing Plan. The PI will make data available to the general scientific community at the conclusion of the study. Given the fact that the entities involved in this application must be HIPAA compliant, de-identification of the data along HIPAA guidelines will guide the development of the final database to be shared. Information should be available to other researchers within 12 months of the conclusion of the study. Since methods of data sharing are just now being developed, it is certainly possible we will have to amend our original plan. However, our current plan would be to have the dataset available via the web through postings of the information on GitHUB. Data will be provided in several “user friendly” statistical formats, including SAS and SPSS. We will also provide a detailed protocol describing study methodology, and a code book describing all data elements in as much detail as possible. The availability of the de-identified data at these web pages would be announced in various journals and publications of interest to clinicians and researchers. In addition to shared information via GitHUB, we will share our data via the National Database for Clinical Trials related to Mental Illness (NDCT; <http://ndct.nimh.nih.gov/>; NOT-MH-14-015 and NOT-MH-15-012). Submission of descriptive data will take place annually (with the year count starting from first date of recruitment of the 1st participant) for the R61 phase given delays due to the COVID-19 pandemic. If the project moves to the R33 phase, data will be submitted bi-annually starting on the second year

of the R33 phase. Submission of all other data is expected at the time of publication, or prior to the end of the grant, whichever occurs first. Raw brain activity including EPI's and T1 images will not be uploaded without removing first all ways of re-constructing participant's faces (de-sculling and removal of soft tissue). Data that has undergone pre-processing may be uploaded. We will share results, positive and negative, specific to the cohorts and outcome measures studied by using the study functionality (see <http://ndct.nimh.nih.gov/results>).

As part of the data sharing, participants and their caregivers will receive periodical updates on any preliminary results as well as milestones achievements as needed. We will also share results via social media such as Facebook and twitter and email participants about posters or publications of the data.

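### Interim results can reach R33 participants and recruits before follow-up ends, and the plan gives two conflicting rules for when data are released

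*Combined protocol and SAP*

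**What the plan says.** **Results to participants and the public.** The Data Sharing Plan (section 21.1) states that "participants and their caregivers will receive periodical updates on any preliminary results as well as milestones achievements as needed". It adds that results will go out on social media and by email. Section 12.1 (Recruitment Process) describes the lab's social-media accounts as a place to tell potential participants about the study, and then says: "These platforms will also be used to disseminate interim findings and progress with participants".

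**Release of data.** The Data Integrity paragraph of section 18 lists as an element of rigour "making all data and analytic algorithms available on a yearly basis for ready access by the wider scientific community using the GitHub platform". The Data Sharing Plan gives a different timetable:

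- General rule: "The PI will make data available to the general scientific community at the conclusion of the study", with access for other researchers within 12 months of that point and GitHub as the intended site.
- National database, R61: "Submission of descriptive data will take place annually".
- National database, R33: "data will be submitted bi-annually starting on the second year" of that phase.
- Everything else: "Submission of all other data is expected at the time of publication, or prior to the end of the grant, whichever occurs first".

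**Outcomes and design.** Section 1 has 70 participants randomised 1:1 in R33 to active NF or Unrelated-NF. Section 3.1 includes the SIQ and C-SSRS among the R33 primary outcomes, alongside imaging, behavioural tasks and self-report scales. The last scheduled assessment is Visit 5, about one month after Visit 4.

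**The concern.** R33 is the part of the programme meant to separate a specific effect of training the chosen locus from the general effect of taking part. The Unrelated-NF arm does that only if both arms have similar expectations throughout. If people who are enrolling, training or still in follow-up learn how R33 is going, several things can change: what they report on the SIQ, what they say in a C-SSRS interview, whether they join, and whether they return for Visit 5. Staff who rate, support or retain participants can be influenced in the same way if they read the same material.

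The conflicting release rules add a practical problem. A data manager following section 18 would post R33 data during accrual; one following section 21.1 would not. Both would be complying with the protocol. A posted result cannot be withdrawn, so the rule needs to be settled before R33 outcome data accumulate.

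**Working it through.** The plan gives no figure on this point, so the check is mainly a comparison of texts.

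**1. Do the updates fall while the trial is running?** Section 12.1 calls the findings interim and section 21.1 calls the results preliminary, so both describe material from before completion. Section 5.2 expects enrolment to take 5 to 10 years, and section 11.1 gives R33 three years. Neither sentence limits the audience to people who have finished Visit 5.

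**2. Is there an embargo elsewhere?** Sections 7, 12.1, 18 and 21.1 contain no rule that withholds comparative R33 results until the last visit or database lock. The separately filed data safety and monitoring plan was not available, so this statement covers only the text seen.

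**3. Release rules side by side.**

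| Item | Section 18, Data Integrity | Section 21.1, Data Sharing Plan |
|---|---|---|
| Open release on GitHub | All data, yearly | At the conclusion of the study |
| National database, R61 | Not addressed | Descriptive data, annually |
| National database, R33 | Not addressed | From year 2 of R33; content not stated |
| All other data | Included in the yearly release | At publication or before the grant ends |

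The first and last rows cannot both be followed. The R33 database row may be meant to cover descriptive data only, because the sentence on all other data follows it, but it does not say so.

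**4. What the conflict amounts to.** Assume that R33 lasts 3 years and that yearly releases fall at the end of each year counted from its start. Under section 18, the releases at the end of years 1 and 2 would precede the end of R33: 3 − 1 = 2 open releases of all data. Under the general rule of section 21.1 there would be none on GitHub before the study concludes.

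**5. From news to bias.** Let *a* and *u* be the mean shifts in ideation change caused by the news in the active and Unrelated-NF arms. Then:

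- observed between-arm difference = true difference + (*a* − *u*)
- observed pre-post change in the active arm = true change + *a*

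If *a* = *u*, the between-arm term is zero and only pre-post change is distorted. If participants guess their arm, *a* and *u* can differ and the contrast is biased by *a* − *u*. Section 4 shows participants a bar that tracks their assigned region, so guessing is conceivable, but that is an inference and not something the documents report.

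**6. Where it would enter the analysis.** In section 18, H2.3 estimates direct and indirect effects of NF on ideation change, so *a* − *u* would enter there. H2.2 relates ideation to connectivity change; a shift shared by everyone would go into the intercept. H1.1 concerns imaging, and H1.2 and H2.1 concern connectivity and the ETB and IAT tasks, so the self-report route applies less directly to them.

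**The case against.** The strongest reply is that the texts promise less than they might seem to.

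- Neither sentence on updates says that arm comparisons will be included. This is true, but neither excludes them, and preliminary results of a two-arm trial would naturally include them.
- The milestones belong to R61, which has no Unrelated-NF arm. Because R33 proceeds only if they are met and uses the better-engaged locus, anyone who knows the design already knows that R61 succeeded. This stands: withholding milestone news would protect little. The exposure that matters is to R33 results.
- News sent to everyone affects both arms and largely cancels in the contrast. This stands unless participants know or guess their arm.
- No text says that raters receive accumulating arm-level results. This also stands. The risk to staff is that they could read what is posted, and the available text places no barrier.

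Three stronger readings are tempting, and the documents do not support them.

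- **That the releases break the blind.** The available text describes no blinding of participants, assessors or analysts, and aggregate news does not tell anyone their own allocation.
- **That section 7.1 contradicts section 21.1.** Section 7.1 says "Results will not be shared with participants unless guardians/parents/caregivers specifically request them in writing", but its context is a one-paragraph summary of an individual's own questionnaires, not aggregate findings.
- **That a false-positive rate can be attached to this.** That would need an assumed differential shift, for which the documents give no basis, and a two-sample test that the Bayesian plan does not use.

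**Conclusion.** The point holds in two parts. First, sections 12.1 and 21.1 commit the study to sending interim and preliminary results to participants, caregivers and the recruitment audience, with no embargo on R33 comparative results in the available text. Secondly, sections 18 and 21.1 contradict each other on when data become public. On the timing assumption above, the difference is two open releases of all data during R33 against none.

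The risk is to R33 outcomes that depend on self-report or interview, chiefly the SIQ and C-SSRS, and to enrolment and retention. The between-arm contrast is biased only if the effect differs by arm; otherwise pre-post change is inflated. The documents do not allow the size to be estimated. The conclusion assumes that no embargo stands in the monitoring plan that was not seen. This should be corrected before R33 outcome data accumulate.

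**What to change.** 1. Reconcile the Data Integrity paragraph of section 18 with the Data Sharing Plan in section 21.1 under one rule: R33 outcome data with arm codes are not publicly released until the last R33 Visit 5 is complete and the database is locked.
2. In sections 12.1 and 21.1, state that until the same point no R33 interim or between-arm outcome result is sent to participants or caregivers or posted on social media. Limit updates during the trial to non-comparative progress, such as recruitment.
3. For national database submissions during R33, state what they contain and how often bi-annually means. Make them without public arm-level outcome data where the repository's rules allow; those rules could not be checked here.

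The first two changes are to wording only. The cost is that R33 data and news become public later, which the Data Sharing Plan's own end-of-study rule already largely accepts. The third may need agreement with the repository.
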